[figure not shown]

**A Research on the Ovarian Function Detection and Protection in
Fertility Preservation Surgery for Ovarian Malignancy**

2019.02.01

Study objectives The primary objective of this study is to identify whether applying GnRHa on patients with ovarian malignancy for fertility preservation surgery preoperatively and postoperatively has a different outcome. By comparing the physical and hormone indexes in the control group and experimental group, we plan to find out the effect of GnRHa.

Trial design This is a prospective interventional trial. After signing of informed consent, the electronic medical data of patients with ovarian malignancy will be collected in this study. 20 patients will be enrolled in this trial. They will be randomized into the control group and the experimental group as to receive GnRHa for fertility preservation surgery preoperatively and postoperatively. We plan to investigate into the effect of GnRHa by monitoring the physical ovarian change and the six hormone indexes in the two different groups.

Sample size The planned sample size was based on data from a previous study, in which the standard deviation was 5. We assumed an one-tailed α error of 0.05 and a sampling error of 1.0. We propose to enroll 24 participants including 12 patients in the control group and the others in the experimental group, and allow for a dropout rate of 10% for an effective sample size of 20.

Inclusion criteria

1. Volunteer to participate in the study with informed consent;
2. Females aged 10-90 who are confirmed with ovarian malignancy and are willing to receive fertility preservation surgery.

Exclusion criteria

1. Suspected or identified as other tumors of genital tract;
2. History of hyperparathyroidism, infectious diseases (tuberculosis, AIDS), autoimmune diseases, or digestive system diseases (malabsorption, crohn disease and dysentery);
3. Other diseases or heavy injuries that will interfere with the results;
4. Simultaneous participation in another clinical study with investigational medicinal product(s) or researcher thinks the subjects are not suitable for this trial.

Withdrawal Subjects must be withdrawn from the study when one of the following criteria occurs:

1. At their own request. At any time during the study and without giving reasons, a subject may decline to participate further. The subject will not suffer any disadvantages as a result;

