2. In the investigator's opinion, continuation of the study treatment would be harmful to the subject's health;
3. Obvious non-compliance;
4. Lost to follow-up;
5. Pregnancy;
6. Other medical or surgical treatments of endometrial carcinoma.

Safety assessments

Safety will be assessed by renal and liver function test, electrolyte, routine blood test. Other indicators are detected during the operation and rehabilitation period. The occurrence of any adverse events in participants will be recorded in the case report forms during each patient visit. We will withdraw patients who have severe adverse events, as it is unsafe for them to continue the trial. Meanwhile, we will give them relevant medical care and follow them up until the reaction has terminated.

Statistic analysis

Before the enrollment of participants, patients' medical data will be collected and analyzed to evaluate whether they are suitable for this trial. With their informed consent, they will be randomized into the control group and the experimental group. The situation of the two group will be almost the same considering the average age, the average BMI, the average grading evaluation. The fertility preservation surgery means the ovary affected by cancerous cell is resected when the other is preserved. If the other side was already resected, the ovarian tumor on the affected side will be removed. Before and after the operation, patients in the control group will receive placebos when the experimental group will receive GnRH_a. The physical ovarian volume, six hormone indexes, AMH and the ovulating period will be monitored and compared by chi-square analysis in SPSS 17.0.

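### Eligibility sets no ovarian-function requirement for a trial of ovarian protection, and one chi-square comparison is named for all outcomes, most of them continuous

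*Combined protocol and SAP*

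**What the plan says.** The title of the combined protocol and SAP gives the subject as "Ovarian Function Detection and Protection". Inclusion criteria, item 2, admits "Females aged 10-90 who are confirmed with ovarian malignancy and are willing to receive fertility preservation surgery"; the only other inclusion item is consent.

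No inclusion or exclusion item mentions menarche, menopause, cycling, AMH or any other sign of ovarian function at entry. The nearest provisions are general:

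- Exclusion item 3: "Other diseases or heavy injuries that will interfere with the results".
- Part of exclusion item 4: "researcher thinks the subjects are not suitable for this trial".
- Statistic analysis, on the review before enrolment: "medical data will be collected and analyzed to evaluate whether they are suitable for this trial".
- Withdrawal, item 5, lists pregnancy, which suggests that mostly fertile patients are expected.

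The analysis is one sentence at the end of Statistic analysis: "The physical ovarian volume, six hormone indexes, AMH and the ovulating period will be monitored and compared by chi-square analysis in SPSS 17.0". The same section says when study treatment is given: "Before and after the operation, patients in the control group will receive placebos when the experimental group will receive GnRH_a".

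**The concern.** A protective effect can be seen only in a patient who has ovarian function to lose. The written criteria admit patients who have none, at either end of the age range. Each such patient takes one of about 20 places, pulls the average treatment difference toward zero and adds variance in the treated arm.

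The analysis sentence adds two difficulties.

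- Chi-square compares counts in categories. Volume, hormone levels and AMH are continuous, so using it means cutting them into categories. The plan names no cut points, and cutting discards information. Nor does a chi-square comparison take account of the value before treatment.
- The ovulating period is not defined. Read as a duration or timing, it has no value in a patient who does not ovulate. Without a rule, who counts in that comparison would be settled after the data are seen.

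**Working it through.** **Text check.** Set each provision that could keep out a patient without ovarian function beside the question of whether it requires her exclusion.

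- Willingness for the surgery: a preference, not a measure of function.
- Exclusion item 3: refers to diseases and injuries; it names no ovarian state.
- Exclusion item 4: discretion, with no threshold.
- Suitability review: stated without criteria.
- Pregnancy withdrawal: acts after entry and says nothing about a patient who cannot conceive.

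All of these allow or encourage exclusion. None requires it.

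**Size of the dilution.** The plan gives no figure on this point to reproduce, so what follows is an illustration.

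Inputs from the documents (Sample size): 20 evaluable patients, taken as 10 per arm, and a one-sided 5% test. Trial design speaks of enrolling 20 and Sample size of enrolling 24 for 20 effective; both lead to 20 here.

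Assumptions: a true effect d of 1 SD in patients with function and nil in a share f without it; the same SD and the same mean in both kinds of patient apart from the effect; comparison by a t test. The share f is not in the documents. One patient in 20 is f = 5%.

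The mean difference becomes (1 − f)d. The treated arm is a mixture of patients who are shifted and patients who are not, so its variance becomes 1 + f(1 − f)d². The control arm keeps variance 1. With d = 1 the average of the two is

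V = 1 + f(1 − f)/2,

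and the effective sample size is

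N_eff = 20(1 − f)²/V.

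- f = 0: 20/1 = 20
- f = 5%: 18.05/1.02375 = 17.6
- f = 10%: 16.2/1.045 = 15.5
- f = 20%: 12.8/1.08 = 11.9

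Power comes from the noncentral t distribution with 18 degrees of freedom, critical value 1.734 and noncentrality (1 − f)/√(0.2V).

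- f = 0: 2.236, power 69.4%
- f = 5%: 2.099, power 64.6%
- f = 10%: 1.969, power 59.8%
- f = 20%: 1.721, power 50.5%

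Simulating 400,000 trials per setting gave 69.3%, 64.7%, 59.8% and 50.4%.

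**Sensitivity to the same-SD, same-mean assumption, at f = 20%.**

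- If patients without function do not vary and share the others' untreated mean, the arm variances are 0.80 and 0.96, average 0.88, and N_eff = 12.8/0.88 = 14.5.
- If they have the same SD but a mean 2 SD away, the control variance is 1 + 0.16 × 4 = 1.64. The treated variance is 1 + 0.16 × 1 = 1.16 or 1 + 0.16 × 9 = 2.44, depending on direction. The averages are 1.40 and 2.04, and N_eff = 9.1 or 6.3. Adjusting for the baseline value would recover part of that loss.

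**Cost of adjusting for two covariates (baseline value and age).** With N = 20 and q = 2, the expected variance factor before any gain is 1 + q/(18 − q − 1) = 1 + 2/15 = 1.133. The break-even R² is 1 − 1/1.133 = 0.118. Residual degrees of freedom go from 18 to 16, and the one-sided 5% critical value from 1.734 to 1.746.

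**The case against.** The best defence is that the age range is a poor guide to who would enrol. A patient must want surgery that preserves fertility, and investigators can refuse anyone they think unsuitable. The share without function may therefore be nil, in which case the dilution is nil too. This stands: the documents show a gap in the criteria, not a demonstrated loss. A reader might infer from the limits of 10 and 90 that a sizeable part of the sample will lack ovarian function. The documents do not support that, and the figures above must not be read as a forecast.

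A second objection is that the outcomes can still be measured in such patients. That is right for volume and AMH. The six hormones are not listed, so nothing is claimed about each of them. A reader might also infer that the ovulating-period comparison is undefined under the plan. That holds only if the measure is a duration or timing. Scored as ovulating or not, which chi-square would suit, a patient who does not ovulate has a value. The underlying defect is the missing definition.

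Third, the expectation that "The situation of the two group will be almost the same considering the average age, the average BMI, the average grading evaluation" might be taken as a further flaw, because nothing beyond randomisation is described to bring it about. Chance imbalance under randomisation is random error, not bias, and a valid test already allows for it. Stratification or minimisation would gain efficiency only, so neither is asked for here.

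Finally, the choice of test is logically separate from eligibility. That is true, but both decide whether these outcomes can show protection, and both can be mended in the same short text.

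**Conclusion.** The point holds on the text. Eligibility does not require the function that the trial sets out to protect, the named test does not suit the continuous outcomes, and the ovulating period has neither a definition nor a rule for a patient who does not ovulate.

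The size of the dilution is unknown because f is unknown. Under the stated assumptions, one patient in 20 without function costs about five percentage points of power, two in 20 about ten, and four in 20 about nineteen. These figures depend on the assumed 1 SD effect and on equal SD and mean; at f = 20% the alternatives examined put the effective sample size anywhere from 6.3 to 14.5. The mismatch between test and continuous outcomes does not depend on f.

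This should be corrected, but nothing here shows that the trial would be biased or that its result would be invalid.

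**What to change.** 1. Reconcile inclusion item 2 with the outcomes by requiring evidence of ovarian function at baseline. The criterion is for the investigators to set.
2. Analyse the continuous outcomes by a linear model adjusted for age and for the value taken before the first study dose. A later pre-operative value could already reflect treatment, because study treatment starts before surgery. Keep chi-square, or an exact test, for categorical outcomes only.
3. State whether the ovulating period is categorical or a duration. Restrict its comparison to patients ovulating at baseline, and count one who stops ovulating after surgery as an unfavourable outcome, not as missing: she is the failure that the trial means to prevent.

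The cost is somewhat narrower accrual, by an amount that is unknown and grows with f; depending on the criterion chosen, it could remove some of the youngest patients whom item 2 now admits. The adjustment uses two residual degrees of freedom and carries about 13% expected variance inflation before any gain, so it pays once baseline value and age together explain more than about 12% of the outcome variance. The rest is a change of text.

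### Withdrawal rules take patients out of the study, not only off study drug, for events that may depend on arm or on ovarian function, and the plan provides for neither later outcome collection nor an analysis set

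*Combined protocol and SAP*

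**What the plan says.** The Withdrawal section is mandatory and concerns the study as a whole: "Subjects must be withdrawn from the study when one of the following criteria occurs". Three of its six items matter here: item 2, where in the investigator's opinion "continuation of the study treatment would be harmful"; item 3, "Obvious non-compliance"; and item 5, pregnancy. Items 1 (own request) and 4 (loss to follow-up) are ordinary dropout.

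Safety assessments adds a further trigger: "We will withdraw patients who have severe adverse events, as it is unsafe for them to continue the trial". These patients receive medical care, and the team will "follow them up until the reaction has terminated". No other follow-up after withdrawal is described.

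Statistic analysis says: "The physical ovarian volume, six hormone indexes, AMH and the ovulating period will be monitored and compared", by chi-square. It also says that "patients in the control group will receive placebos" while the experimental group receives GnRHa. It names no analysis population, does not say that patients are analysed as randomised, and gives no rule for missing outcomes.

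On numbers, Trial design says "20 patients will be enrolled in this trial". Sample size gives 24 enrolled, 12 per arm, with 10% dropout and an effective size of 20.

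**The concern.** The plan never separates stopping study drug from leaving the study. Followed as written, a patient who stops drug because of harm, who does not comply or who becomes pregnant leaves the trial, and nothing provides for measuring her outcomes afterwards.

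Each of these events happens after randomisation. Harm, severe adverse events and non-compliance may differ between GnRHa and placebo. Pregnancy is tied to the outcome: in a trial about protecting ovarian function, the rule removes a patient at the point where she shows that function. If the comparison is then made among those who remain, the two groups may differ for reasons that randomisation no longer balances. With no analysis set fixed in advance, the choice of whom to count could also be made after results are known.

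**Working it through.** **1. The plan's own dropout figure.** Inputs from Sample size: effective size 20, dropout 10%. In total, 20/(1 − 0.10) = 22.2, which rounds up to 23. Per arm, 10/0.9 = 11.1; taking 12 per arm gives the stated 24. The step from 20 to 24 is thus a rounded-up allowance. The 4-patient gap (4/24 = 16.7%) should not be read as the expected loss. The stated 10% is 0.10 × 24 = 2.4 patients, or 0.10 × 20 = 2.0 if 20 are enrolled: about two. It is not split by reason, so it also covers own request and loss to follow-up.

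**2. Weight of each patient.** The share of an arm is m/n, for m lost of n. The arm of 10 assumes that 20 are enrolled with equal allocation.

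| Lost from one arm | n = 12 | n = 10 |
|---|---|---|
| 1 | 8.3% | 10.0% |
| 2 | 16.7% | 20.0% |

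**3. Effect of leaving patients out.** Let d be the mean of those lost minus the mean of those remaining. Then

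mean of all n − mean of remaining = (m/n) × d.

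For a yes/no outcome, d lies between −1 and 1, so the percentages above are also the largest possible shift in that arm's proportion, in percentage points.

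For a continuous outcome, take the plan's SD of 5 (variable and unit not named) and assume d of 0.5, 1 or 2 SD, that is 2.5, 5 or 10:

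| | d = 2.5 | d = 5 | d = 10 |
|---|---|---|---|
| 1 of 12 | 0.21 | 0.42 | 0.83 |
| 2 of 12 | 0.42 | 0.83 | 1.67 |
| 1 of 10 | 0.25 | 0.50 | 1.00 |
| 2 of 10 | 0.50 | 1.00 | 2.00 |

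**4. Comparison with random error.** The standard error of a difference in means is 5 × √(2/n): 2.04 for n = 12 and 2.24 for n = 10. The largest ratios are 1.67/2.04 = 0.82 and 2.00/2.24 = 0.89. Within the assumed range, two losses shift the mean by less than one standard error. The shift grows in proportion to the number lost.

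**5. Is 2 SD a reasonable upper end?** In a simulation of normal data with SD 5 and 12 per arm, removing the lowest one or two values in an arm shifts its mean by 0.74 or 1.38. Solving for d gives 0.74 × 12 = 8.9 (1.8 SD) and 1.38 × 12/2 = 8.3 (1.7 SD). Even this constructed extreme falls, on average, inside the range used.

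**The case against.** The strongest reply is that no bias has been shown. The plan does not forbid later measurement or say that data obtained before withdrawal are discarded. The arithmetic gives withdrawn patients zero weight, which the text does not require. It works mainly in means, using an SD whose variable is not named, while the only test planned is chi-square. It also charges the whole 10% dropout to the disputed triggers, although own request and loss to follow-up are part of it and no wording change recovers them. Giving placebo to controls may reduce differences in compliance between arms, though blinding is not stated.

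Most of this stands as a limit on size: the figures are illustration only. It does not remove the point. The withdrawal rule is stated and mandatory, and it takes randomised patients out for reasons that can depend on arm or outcome. Silence on the analysis set leaves the consequence open.

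A reader might infer from the effective size of 20 that withdrawn patients will be dropped from the analysis. That is a planning allowance, not an analysis rule. A reader might also infer that withdrawal item 6, on treatment of endometrial carcinoma, contradicts exclusion 1. The exclusion bars other genital-tract tumours at entry, whereas item 6 can be read as covering a patient treated for one later, so the two can be read as compatible.

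**Conclusion.** The point holds as a design weakness that should be corrected. As written, the rules end study participation for treatment harm, non-compliance, pregnancy and severe adverse events, with only safety follow-up described and no analysis set, so a comparison of remaining patients can be biased.

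It is tempting to go further and say that the result will be biased, or biased towards GnRHa. The documents do not support that. How many patients each trigger will remove, from which arm, and how they would differ are all unknown, and the triggers could pull in opposite directions. What the documents do fix is the weight of a patient: 8.3% of an arm of 12, or 10% of an arm of 10. The shifts of 0.21 to 2.00, against standard errors of 2.04 or 2.24, rest on an assumed difference of 0.5 to 2 SD, full exclusion of those lost, and the unnamed SD of 5.

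The reference to endometrial carcinoma in item 6 fits poorly with an ovarian-malignancy population and needs reconciling, but it is a separate wording matter and adds nothing to this bias argument.

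**What to change.** Leave every rule on when study drug stops, and the severe-adverse-event safety rule, as they stand. Then:

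- State that stopping study drug is distinct from leaving the study. Continue to collect ovarian volume, the six hormones, AMH and ovulating period unless the patient withdraws consent or the investigator judges the measurement unsafe.
- Keep all data obtained before withdrawal.
- Analyse all randomised patients with outcome data by assigned arm.
- Report withdrawals by arm and reason.
- Treat a pregnancy as evidence that ovulation occurred, not as a missing outcome, and do not use hormone values taken during pregnancy. The date on which a pregnancy is recorded should not stand in for the date of ovulation.
- Specify one simple sensitivity analysis for missing outcomes.

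Separately, reconcile the wording of withdrawal item 6 with the trial's disease.

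The cost is a few sentences of protocol text and limited extra follow-up for a few patients; with no visit schedule in the plan, the amount cannot be stated. Recovery will be partial. Losses from own request or loss to follow-up remain, pregnancy still leaves hormone values missing, and little may be gained for non-compliance, which is not defined, if it means missed visits.

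### Chi-square is the only analysis named for ovarian volume, six hormones and AMH, although these are continuous measures and no cut-points are given; the assertion that the arms will be alike needs rewording

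*Combined protocol and SAP*

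**What the plan says.** The document is a combined protocol and SAP, and the Statistic analysis section is the whole of its analysis plan. The method is given in one sentence: "The physical ovarian volume, six hormone indexes, AMH and the ovulating period will be monitored and compared by chi-square analysis in SPSS 17.0". No cut-points, other test, model or covariate is named, and no measurement times are given.

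On allocation, the section says "With their informed consent, they will be randomized into the control group and the experimental group". It then states, as a result and not as a method: "The situation of the two group will be almost the same considering the average age, the average BMI, the average grading evaluation". No stratification, blocking, minimisation, matching or balance tolerance is described.

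The Sample size section adds "We assumed an one-tailed α error of 0.05" and "The planned sample size was based on data from a previous study, in which the standard deviation was 5". It does not say which outcome that SD belongs to. It plans 24 enrolled (12 per arm) and 20 effective, whereas Trial design gives 20 enrolled.

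**The concern.** Ovarian volume, hormone levels and AMH are measured on continuous scales, and chi-square compares counts in categories. To follow the plan as written, someone must first choose cut-points. Nothing fixes these in advance, so they could be chosen after the data are seen. Dichotomising also discards information, which a trial of 20 to 24 patients can ill afford.

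Plain chi-square also has no place for a pre-treatment value or for age, and eligibility runs from 10 to 90 years. If the arms differ in mean age by 0.5 SD, the unadjusted difference moves by 0.5 × r SD, where r is the correlation of the outcome with age (not given in the plan). Without a prespecified adjusted analysis, such a result would be hard to interpret. The balance sentence suggests that this cannot arise, but randomising so few patients does not prevent it.

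The ovulating period is left out of this point. The plan does not say whether it is a yes/no, a date or a duration, and for a yes/no outcome chi-square or an exact test could fit.

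**Working it through.** **Numbers per arm.** The plan's dropout step reproduces: 10 / (1 − 0.10) = 11.1, rounded up to 12 per arm, or 24 in total. Whether 20 follows from the stated SD and sampling error is a separate question and is not needed here. Both 10 and 12 per arm are used below.

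**Error rate of chi-square after a pooled-median split (assumed cut-point).** With n per arm, if a patients in one arm lie above the median, n − a do in the other. Then:
- uncorrected chi-square = 4(a − n/2)² / (n/2);
- continuity-corrected chi-square = 4(a − n/2 − 0.5)² / (n/2);
- exact one-sided tail = Σ C(n, j)² / C(2n, n) for j ≥ a.

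The critical value is 2.706 for one-tailed 0.05 and 3.84 for two-sided 0.05.

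- n = 10, a = 7: uncorrected 3.2, corrected 1.8; tail = 16,526 / 184,756 = 8.9%.
- n = 10, a = 8: uncorrected 7.2, corrected 5.0; tail = 2,126 / 184,756 = 1.2%.
- n = 12, a = 8: uncorrected 2.67, corrected 1.5; neither version rejects.
- n = 12, a = 9: uncorrected 6.0, corrected 4.17; tail = 52,901 / 2,704,156 = 2.0%.

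With 10 per arm and one-tailed 0.05, the uncorrected test rejects from 7 v 3, so its true error is 8.9%. The corrected test rejects from 8 v 2, with true error 1.2%. Two-sided, both versions first reject at 8 v 2, and the true error is 2 × 1.15% = 2.3%. With 12 per arm, both versions first reject at 9 v 3 under either sidedness.

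**Power at a true difference of 1 SD, normal outcomes (both assumed; simulation).**

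| Per arm | Sidedness | Chi-square, median split | Comparison of means |
|---|---|---|---|
| 10 | one-sided | 30% (corrected) | 69% |
| 10 | two-sided | 30% | 56% |
| 12 | one-sided | 45% | 77% |
| 12 | two-sided | 45% | 65% |

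The uncorrected one-tailed test with 10 per arm has 67% power, but at a true error of 8.9%.

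**Sensitivity.** With 10 per arm, one-sided, the comparison is 46% against 85% at 1.25 SD and 63% against 94% at 1.5 SD. If outcomes are log-normal (log-SD 1, shift of 1 log-SD, assumed), the median split stays at 30%. A comparison of raw-scale means falls to 55% one-sided and 37% two-sided. With 12 per arm, two-sided, the two methods tie at 45%.

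**What adjustment costs and gains (20 analysable, k covariates, R² = share of variance explained).** The one-sided 95% margin in outcome SDs is t(0.95, 18 − k) × √0.2 × √[(1 − R²) × 17/(17 − k)].
- k = 0: 1.734 × 0.447 = 0.775.
- k = 2: 0.831, 0.720 and 0.588 at R² = 0, 0.25 and 0.5 (assumed range).
- Width ratio at R² = 0: 0.831 / 0.775 = 1.072. Break-even R² = 1 − 1/1.072² = 0.13.
- One-sided power at 1 SD with two covariates: 65%, 75% and 88% at the same R² values.

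Margins are in SD units because the plan's SD of 5 is tied to no outcome.

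**Balance.** The SE of a standardised mean difference is √(2/10) = 0.447, or √(2/12) = 0.408. The probability of a gap above 0.5 SD (this review's cut-off) on one factor is 26% with 10 per arm and 22% with 12. For at least one of three independent factors it is 1 − (1 − 0.264)³ = 60%, or 53% with 12. At pairwise correlation 0.5 these become 54% and 47%, and they cannot fall below the one-factor figures.

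**The case against.** The strongest reply is that the size of the loss depends on assumptions outside the plan, and that stands. The one-tailed error appears only under Sample size. The Statistic analysis section states no sidedness, and the study objective asks whether outcomes differ, which is not directional. A reader might infer that chi-square must either break the 5% error or lose more than half the power. The documents do not support this. Two-sided, the true error is 2.3% and the power is 54% of that for a comparison of means (30 / 56). One-sided, the ratio is above one half at 1.25 SD (46 / 85) and with 12 per arm (45 / 77). For skewed outcomes, a raw-scale comparison of means loses part of its advantage one-sided and most or all of it two-sided, so a linear model without a suitable scale would not be a clear gain.

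A reader might also infer that chi-square can never adjust for an imbalance. A stratified (Mantel-Haenszel) version could adjust for a coarse category. The plan does not name it, however, and with 20 patients its tables would be very sparse.

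Finally, a reader might take chance imbalance to bias the trial. It does not: the randomised comparison is unbiased on average, and only precision and interpretability suffer. The balance sentence may express an expectation, in which case it is unsupported, or an intention, in which case the method is missing.

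None of this answers the main point. Chi-square is assigned to continuous measures without cut-points, whatever the sidedness, effect size or distribution.

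**Conclusion.** The point holds as a mismatch between test and outcome. For ovarian volume, six hormones and AMH, the named analysis cannot be run without cut-points that the plan does not give, and the plain test uses neither baseline nor age. Under a pooled-median split, normality and a 1 SD effect, power with 10 per arm is 30% against 56% (two-sided) or 69% (one-sided, continuity-corrected). The 8.9% error belongs only to the uncorrected one-tailed test with 10 per arm. These figures are illustrations, not properties of the trial, since the plan gives neither cut-points nor an effect size.

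The balance sentence is a secondary matter of wording. No mechanism in the plan secures what it says, but the validity of the comparison does not depend on it.

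**What to change.** 1. Replace chi-square for the continuous outcomes with a prespecified linear model (ANCOVA) at one named post-treatment time point. Adjust for age and for the value taken before the first GnRHa or placebo dose. Report the adjusted difference with its confidence interval. The baseline must precede dosing because "Before and after the operation, patients in the control group will receive placebos", and the experimental arm is dosed over the same period, so a later pre-operative value may already reflect treatment.
2. Analyse hormones and AMH on the log scale, or name a rank-based test as fallback.
3. For volume, use the pre-dose volume of the retained ovary only. The plan describes two situations: "The fertility preservation surgery means the ovary affected by cancerous cell is resected when the other is preserved" and "If the other side was already resected, the ovarian tumor on the affected side will be removed". If any patient has tumour removed from the retained ovary, adjust the volume model for age alone in all patients.
4. Replace the balance sentence with: *Baseline characteristics, including age, BMI and grade, will be tabulated by arm.* BMI and grade are better tabulated than modelled: four covariates widen the interval by 16% if they explain nothing, and pay off only above about 26% of variance explained.

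**Cost.** Two of 18 degrees of freedom with 20 analysable patients; an interval about 7% wider than an unadjusted comparison of means if the covariates explain nothing, and narrower above about 13%; and one baseline measurement per outcome if none is already taken. With age alone, the cost is one degree of freedom and about 3% in width.

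Stratifying the allocation by age is not part of this fix. It could lower the chance of an age gap above 0.5 SD from 26% to about 9% with 20 patients, but that assumes a split at the median age, which is unknown before enrolment. The change also leaves open which of the eight outcomes is primary and how multiplicity is handled.

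### Two operations that leave different amounts of ovarian tissue are pooled with no stratification or adjustment, which costs precision and exposes a 24-patient trial to chance imbalance

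*Combined protocol and SAP*

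**What the plan says.** The Statistic analysis section describes the usual operation as removal of the diseased ovary with the other left in place, then adds a second case: "If the other side was already resected, the ovarian tumor on the affected side will be removed". Patients of both kinds are randomised to GnRHa or placebo. The outcomes, beginning with "The physical ovarian volume" and going on to six hormones, AMH and the ovulating period, are to be compared by chi-square. No stratum, covariate or subgroup for operation type appears, and no blocking, stratification or minimisation is described.

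On comparability the same section states: "The situation of the two group will be almost the same considering the average age, the average BMI, the average grading evaluation". It gives no method for achieving this, and operation type is not in the list.

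On numbers, the Sample size section says "We propose to enroll 24 participants including 12 patients in the control group and the others in the experimental group", and that the plan will "allow for a dropout rate of 10% for an effective sample size of 20". The Trial design section instead says "20 patients will be enrolled in this trial". I use 12 per arm below and note what changes at 10.

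**The concern.** The outcomes measure ovarian tissue and function, and the two operations leave different amounts of tissue: a whole ovary in one case, the remainder of an only ovary in the other. Operation type is therefore likely to predict volume, AMH and hormones, possibly strongly. Ignoring it has two consequences. Its effect goes into the error term and reduces power in a trial with little to spare. And if one arm happens to receive more only-ovary patients, that particular trial's result is shifted by surgery as well as by treatment.

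Volume has a further problem. The plan does not say which ovary is measured, or when. In an only-ovary patient, the ovary present before surgery carries the tumour, so any comparison that used the pre-operative volume would mix tumour removal with ovarian change.

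**Working it through.** **Inputs from the plan.** 12 per arm; 10% dropout; 20 evaluable; SD 5 (variable and unit not named); one-tailed α 0.05; sampling error 1.0.

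**Inputs assumed, because the plan does not give them.** The share p of patients with only one ovary, from 5% to 50%; the effect of operation type on an outcome, 1 or 2 SD.

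**The plan's own size.** The dropout step reproduces: 10/0.9 = 11.1, rounded up to 12 per arm, or 24. The precision does not. The plan says "The planned sample size was based on data from a previous study, in which the standard deviation was 5" and "We assumed an one-tailed α error of 0.05 and a sampling error of 1.0". For a single mean this needs (1.645 × 5/1.0)² = 67.6, so 68 patients; for a difference of two means, 2 × 67.6 = 135.3, so 136 per arm. At 12 per arm the standard error of the difference is 5 × √(2/12) = 2.04, or 0.41 SD. The figure of 1.0 is therefore not a usable yardstick here; the standard error is.

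**Imbalance in operation type.** Take the number of only-ovary patients in each arm as independent Binomial(12, p). The chance that the arms differ by 3 or more is:

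| p | 5% | 10% | 20% | 30% | 40% | 50% |
|---|---|---|---|---|---|---|
| Probability | 2% | 8% | 20% | 26% | 30% | 31% |

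A second model, with arms fixed at 12 and exactly K only-ovary patients among 24 (hypergeometric), gives a difference of 4 or more with probability 9% (K = 4), 16% (K = 6), 19% (K = 8) and 22% (K = 12).

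**Effect on the estimate.** Shift = (imbalance/12) × operation effect.
- 3 patients, 1 SD: 3/12 × 1 = 0.25 SD; 0.25/0.41 = 0.6 standard errors.
- 3 patients, 2 SD: 3/12 × 2 = 0.5 SD; 0.5/0.41 = 1.2 standard errors.

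**Validity and power.** These come from a simulation (40,000 runs, 12 v 12, two-sided 0.05) of an unadjusted t-test against a linear model with operation type. With no treatment effect, the unadjusted test rejects in about 5% of trials overall. Among trials with an imbalance of 4 or more it rejects in 9% (K = 6, 1 SD), 19% (K = 6, 2 SD) or 17% (K = 12, 2 SD). With an assumed true effect of 1.2 SD, power is:

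| K | Operation effect | Unadjusted | Adjusted |
|---|---|---|---|
| 6 | 1 SD | 73% | 78% |
| 6 | 2 SD | 55% | 78% |
| 12 | 2 SD | 50% | 78% |

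**The promised balance.** For a continuous covariate, the standardised difference in means has SD √(2/12) = 0.41. The chance that it exceeds 0.5 in either direction is 2 × [1 − Φ(0.5/0.408)] = 22%. At 10 per arm the SD is √(2/10) = 0.45 and the chance is 26%.

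**The case against.** A reader might infer that pooling the operations biases the trial, or that any imbalance would pass for a GnRHa effect. The documents do not support that. Allocation is randomised, so the unadjusted comparison is right on average and its error rate already allows for chance imbalance; the simulation confirms about 5% overall. With the stated one-tailed test, only imbalance in one direction could mimic benefit (about 13% rather than 26% at a 30% share); the other direction would mask it. This objection stands: the harm is lost precision, plus a distorted result in those trials that happen to be unbalanced.

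A second tempting reading sets a shift of 0.25 SD (1.25 units at SD 5) against the stated sampling error of 1.0. It fails because 24 patients do not deliver 1.0; against the actual standard error of 2.04, the shift is modest. The unit behind the SD is also unknown.

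A third objection is that the second operation may be rare, since the plan presents it as a conditional case. That is fair: at a 5% share, about 1 patient in 24, a difference of 3 or more has only a 2% chance.

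Finally, one might infer that volume will be analysed as a before-after change contaminated by tumour. The plan refers to monitoring ovarian change and comparing volume, but never defines a difference. What is supported is that the volume outcome is undefined.

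**Conclusion.** The point holds as a worthwhile, low-cost improvement, not as a flaw that invalidates the comparison. Operation type is an obvious predictor of these outcomes, and it can be established from surgical history before randomisation, yet neither the allocation nor the analysis uses it.

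The size depends on two quantities absent from the documents. If few patients have only one ovary, little is lost. If 20% or more do and the operation effect is 1 to 2 SD, a 3-patient imbalance arises in a fifth to a third of trials, and in the simulated cases (6 or 12 of 24 patients) ignoring operation type costs about 5 to 28 percentage points of power. The power figures also rest on the assumed treatment effect of 1.2 SD.

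The assertion of near-equal groups on age, BMI and grade should not stand as written: randomising 24 patients does not assure it, and no method is offered. The 22% treats each covariate as continuous, which is approximate for grade.

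**What to change.** 1. Randomise in permuted blocks stratified by operation type (one ovary to be kept whole, or tumour removed from an only ovary).
2. For the continuous outcomes, replace chi-square, which has no place for covariates and does not suit such data, with a linear model (ANCOVA) of the postoperative value on arm, operation type and age; eligibility spans 10 to 90 years. For AMH and the hormones, add the pre-treatment value.
3. Define the volume outcome as the postoperative volume of the remaining ovary, at a stated time. Do not adjust it for the pre-treatment volume of a tumour-bearing ovary, which would bring the tumour back in through the covariate.
4. Replace the sentence promising similar groups with this method, and tabulate baseline characteristics, including operation type, by arm.

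**Cost.** Two allocation lists, one of which may hold only a few patients. Beyond arm, the model uses two degrees of freedom for volume and three for AMH and hormones. With 20 evaluable patients, residual degrees of freedom fall from 18 to 16 or 15, so no further covariates should be added. Surgery, treatment and data collection need not change, apart from fixing when and on which ovary volume is recorded.
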